## **Glossary of terms**

Additional treatment	Medicinal products that may be used during the clinical trial as described in the protocol, but not as an investigational medicinal product (e.g., any background therapy)
Assessment	A procedure used to generate data required by the study
Biologic Samples	A biological specimen including, for example, blood (plasma, serum), saliva, tissue, urine, stool, etc. taken from a study participant
Clinical Outcome Assessment (COA)	A measure that describes or reflects how a participant feels, functions, or survives
Coded Data	Personal Data which has been de-identified by the investigative center team by replacing personal identifiers with a code.
Cohort	A group of individuals who share a common exposure, experience or characteristic, or a group of individuals followed up or traced over time
Control drug	A study drug (active or placebo) used as a comparator to reduce assessment bias, preserve blinding of investigational drug, assess internal study validity, and/or evaluate comparative effects of the investigational drug
Discontinuation from study	Point/time when the participant permanently stops receiving the study treatment and further protocol required assessments or follow-up, for any reason. No specific request is made to stop the use of their samples or data.
Discontinuation from study treatment	Point/time when the participant permanently stops receiving the study treatment for any reason (prior to the planned completion of study drug administration, if any). Participant agrees to the other protocol required assessments including follow-up. No specific request is made to stop the use of their samples or data.
Dosage	Dose of the study treatment given to the participant in a time unit (e.g., 100 mg once a day, 75 mg twice a day)
Electronic Data Capture (EDC)	Electronic data capture (EDC) is the electronic acquisition of clinical study data using data collection systems, such as Web-based applications, interactive voice response systems and clinical laboratory interfaces. EDC includes the use of Electronic Case Report Forms (eCRFs) which are used to capture data transcribed from source data/documents used at the point of care
End of the clinical trial	The end of the clinical trial is defined as the last visit of the last participant or at a later point in time as defined by the protocol

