- Effect on platelet function risk for bleeding: BTK is a signaling molecule in one of several platelet activation pathways, and clinically relevant effects of remibrutinib on platelet functions were observed in the remibrutinib preclinical toxicology program. The mode of action by which remibrutinib could potentially cause bleeding is currently not fully understood. In vitro assessments suggest a target-related impact on platelets, similar to effects induced by the BTK inhibitor ibrutinib, which has been shown to inhibit clot retraction (Bye et al 2015).
- In CSU, in the completed core CLOU064A2201 Phase 2b study, 18 (6.7%) non-serious bleeding events were reported in any remibrutinib arm compared to one event on placebo (2.4%); none of the AEs was serious or severe. All the bleeding AEs reported were mild, except 2 moderate AEs: gingival bleeding and hematuria. Two bleeding events (petechiae and hematuria) led to study treatment discontinuation. There were no notable clinically relevant abnormalities for coagulation parameters, hemoglobin levels or platelet counts noted in these studies. In the interim analysis of the open-label long-term (up to 52 weeks) extension trial CLOU064A2201E1, the rate of bleeding events (4.4%) was comparable to that seen in the core trial; all events were non-serious, and all but 2 events (purpura and heavy menstrual bleeding in the setting of leiomyoma) were mild in severity. Potential effects of remibrutinib on hemostasis should be monitored both clinically and by standard, validated laboratory measures including complete blood count and standard coagulation parameters. Clinical monitoring should focus on skin (bruising, petechiae) and mucosa (e.g., gastro-intestinal (GI) tract bleeding including gingival, rectal, and conjunctival bleeding). Patients with a known history of bleeding disorders, or with a history of clinically relevant gastrointestinal bleeding and patients requiring anti-platelet or anticoagulant therapy (other than aspirin up to 100 mg/d or clopidogrel up to 75 mg/d) are excluded from the trial; the use of dual anti-platelet therapy (e.g., acetylsalicylic acid + clopidogrel) is prohibited (see details in Section 5.2 and Section 6.2.2). In case of a significant bleeding event, study treatment must be discontinued immediately. Please refer to the current IB for further details

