Reproductive toxicity: Remibrutinib is not genotoxic or mutagenic in in vitro or in vivo studies. No effects on fertility or embryo-fetal development were observed in rats up to the highest dose, while in rabbits a no-observed-adverse-effect-level at 100 mg/kg/day was established. At doses ≥300 mg/kg/day, body weight loss, marked low food consumption, and moribundity were noted, as well as a higher incidence of external fetal malformations (see details in IB). For the approved BTK inhibitors, embryo-fetal toxicity in animals is reported (see national prescribing information). Highly effective methods of contraception must be practiced. Women of child-bearing potential will be informed that taking the study treatment may involve unknown risks to the fetus if pregnancy were to occur during the trial and must agree that in order to participate in the trial they must adhere to the contraception requirements outlined in the exclusion criteria. If there is any question that the participant will not reliably comply, they should not be entered or continue in the study.

For detailed information on potential risks associated with remibrutinib, please refer to the IB.

In summary, CSU patients with inadequate response to H1-antihistamines (and other available treatment options if applicable) participating in this clinical trial may significantly benefit from treatment with remibrutinib. Additionally, this trial will help to improve the understanding of remibrutinib in the management of CSU and potentially enable the development of a novel, innovative, oral drug that could improve the quality of life of CSU patients beyond the limited treatment modalities currently available. Potential risks are mitigated as far as possible by compliance with inclusion/exclusion criteria, study procedures, very close clinical and laboratory monitoring, periodic review of safety data by an independent Data Monitoring Committee (DMC), and study drug discontinuation rules. As with investigational drugs in general, not all safety risks are known. Participants and investigators participating in this trial will be informed should important new safety information become available.

Considering all aspects, the risk-benefit assessment fully supports this trial with remibrutinib 25 mg b.i.d.

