- 11. Women of child-bearing potential (WoCBP), defined as all women physiologically capable of becoming pregnant, unless they are using highly effective methods of contraception during dosing and for 7 days after stopping of study treatment. Highly effective contraception methods include:
  - Total abstinence (when this is in line with the preferred and usual lifestyle of the participant). Periodic abstinence (e.g., calendar, ovulation, symptothermal, postovulation methods) and withdrawal are not acceptable methods of contraception
  - Female sterilization (have had surgical bilateral oophorectomy with or without hysterectomy) total hysterectomy or bilateral tubal ligation at least six weeks before taking investigational drug. In case of oophorectomy alone, only when the reproductive status of the woman has been confirmed by follow up hormone level assessment
  - Male sterilization (at least 6 months prior to screening). For female participants on the study, the vasectomized male partner should be the sole partner for that participant
  - Use of oral (estrogen and progesterone), injected or implanted hormonal methods of contraception

In case of use of oral contraception, women should have been stable on the same pill for a minimum of 3 months before taking investigational drug.

are considered post-menopausal if they have had 12 months of natural (spontaneous) amenorrhea with an appropriate clinical profile (e.g., age appropriate, history of vasomotor symptoms). Women are considered not of child-bearing potential if they are post-menopausal or have had surgical bilateral oophorectomy (with or without hysterectomy), total hysterectomy or bilateral tubal ligation at least six weeks ago. In the case of oophorectomy alone, only when the reproductive status of the woman has been confirmed by follow up hormone level assessment is she considered not of child bearing potential.

If local regulations deviate from the contraception methods listed above to prevent pregnancy, local regulations apply and will be described in the informed consent form (ICF).

- 12. Major surgery within 8 weeks prior to screening or planned surgery for the duration of the study
- 13a. History of live attenuated vaccine within 6 weeks prior to baseline or requirement to receive these vaccinations at any time during the study

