- 14. Evidence of clinically significant cardiovascular (such as but not limited to myocardial infarction, unstable ischemic heart disease, NYHA Class III/IV left ventricular failure, arrhythmia and uncontrolled hypertension within 12 months prior to Visit 1), neurological, psychiatric, pulmonary, renal, hepatic, endocrine, metabolic, hematological disorders, gastrointestinal disease or immunodeficiency that, in the investigator's opinion, would compromise the safety of the participant, interfere with the interpretation of the study results or otherwise preclude participation or protocol adherence of the participant
- 15. Uncontrolled disease states, such as asthma, or inflammatory bowel disease, where flares are commonly treated with oral or parenteral corticosteroids
- 16. Hematology parameters at screening:
  - Hemoglobin: < 10 g/dL
  - Platelets: < 100 000/mm^3
  - Leucocytes: <3 000/mm^3
  - Neutrophils: < 1 500/mm^3
- 17. Significant bleeding risk or coagulation disorders
- 18a. History of gastrointestinal bleeding, e.g., in association with use of nonsteroidal antiinflammatory drugs (NSAIDs), that was clinically relevant (e.g., for which intervention was indicated or requiring hospitalization or blood transfusion)
- 19a. Requirement for anti-platelet medication, except for acetylsalicylic acid up to 100 mg/d or clopidogrel up to 75 mg/d. The use of dual anti-platelet therapy (e.g., acetylsalicylic acid + clopidogrel) is prohibited.
- 20. Requirement for anticoagulant medication (e.g., warfarin or Novel Oral Anti-Coagulants (NOAC))
- 21. History or current hepatic disease including but not limited to acute or chronic hepatitis, cirrhosis or hepatic failure or Aspartate Aminotransferase (AST)/ Alanine Aminotransferase (ALT) levels of more than 1.5 x upper limit of normal (ULN) or International Normalized Ratio (INR) of more than 1.5 at screening
- 22. History of renal disease, creatinine level above 1.5x ULN, or estimated Glomerular Filtration Rate (eGFR) <45 ml/min (using the Cockcroft-Gault equation) at screening
- 23. Evidence of an ongoing Hepatitis C infection (e.g., defined by the detection of hepatitis C-ribonucleic acid (HCV-RNA) at screening) and/or an ongoing Hepatitis B infection (defined by the detection of Hepatitis B virus surface antigen (HBsAg) and/or hepatitis B virus (HBV)-DNA at screening; participants who are positive for anti-hepatitis B core

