Other immunosuppressive/immunomodulating medication with or without known effect on CSU including but not limited to hydroxychloroquine, methotrexate, cyclosporine A, cyclophosphamide, tacrolimus and mycophenolate mofetil	30 days or 5 half-lives (whichever is longer) prior to screening until end of treatment 	Discontinue immunosuppressive/ immunomodulating medication if medically justifiable and closely monitor for potential associated adverse events. If discontinuation not possible, discontinue study treatment.
Intravenous (i.v.) immunoglobulins or plasmapheresis	30 days prior to screening until end of treatment 	Discontinue i.v. immunoglobulins or plasmapheresis if medically justifiable and closely monitor for potential associated adverse events. If discontinuation not possible, discontinue study treatment.
Ultraviolet (UV) therapy	From screening until end of treatment 	Discontinue UV therapy and closely monitor for potential associated adverse events.
Any other therapy intended for the treatment of urticaria including but not limited to herbal therapies	From 2 weeks prior to the first administration of study treatment until end of treatment 	Discontinue any therapy intended for the treatment of urticaria and closely monitor for potential associated adverse events.
Live attenuated vaccines	6 weeks prior to baseline until at least 4 weeks after last dose of study treatment	Discontinue study treatment.
Strong inhibitors of CYP3A4	From 2 weeks prior to the first administration of study treatment until end of treatment 	Discontinue CYP3A4 inhibitor if medically justifiable and closely monitor for potential associated adverse events. If discontinuation

Medication	Prohibition period	Action taken
		not possible, discontinue study treatment
Moderate and strong inducers of CYP3A4	From 2 weeks prior to the first administration of study treatment until end of treatment 	Discontinue CYP3A4 inducers if medically justifiable and closely monitor for potential associated adverse events. If discontinuation not possible, discontinue study treatment.
Anticoagulant medication (e.g., warfarin, or NOAC)	From screening until end of treatment 	Only if medically justifiable, discontinue anticoagulant medication and interrupt study medication until anticoagulant effects have ended. Otherwise discontinue study treatment. Closely monitor coagulation parameters and associated adverse events.

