**Novartis** 

Investigational or other study treatment dose adjustments are not permitted.

Study treatment interruptions are permitted in order to manage the following events:

- Management of bleeding events: in case of planned surgery with clinical significant bleeding risk, interruption of study treatment 7 days before the surgery is required; after recovery, participant may re-start study treatment after 7 days.
- Management of participants in case of Hepatitis B re-activation (new appearance of detectable HBV-DNA or positive HBsAg): participants should start antiviral treatment according to local clinical practice and interrupt study treatment until HBV-DNA and HBsAg reach an undetectable level, and then re-start study treatment.

Study treatment interruption for other than the above reasons is only permitted if, in the opinion of the investigator, a participant is deemed to be at a significant safety risk unless administration of investigational treatment is temporarily interrupted. In such cases study treatment should be interrupted only during the time that this risk is present and ongoing. Study treatment can be restarted at the next scheduled visit after resolution of the safety risk.

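### Section 4.5 requires a permanent stop after any significant bleed, but the bleeding item in 9.1.1 and the restart clause in 6.6 do not carry that rule through

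*Protocol*

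**What the plan says.** **The rule.** Protocol Section 4.5, in its paragraph on platelet function and bleeding, says: "In case of a significant bleeding event, study treatment must be discontinued immediately". The sentence is not limited to spontaneous bleeds and does not ask whether the investigator thinks the participant can continue. Table 6-2 repeats it in the anticoagulant and anti-platelet rows. The closing summary of 4.5 lists periodic safety review "and study drug discontinuation rules" among the ways in which risk is mitigated.

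**What discontinuation means.** The Glossary defines discontinuation from study treatment as "Point/time when the participant permanently stops receiving the study treatment for any reason", and Section 9.1.1 defines it in the same sense. Table 6-2 treats interruption as a separate action: in the anticoagulant row the site may stop the anticoagulant and "interrupt study medication until anticoagulant effects have ended", and must otherwise discontinue study treatment.

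**Section 9.1.1.** This section lists the circumstances in which discontinuation is required. Bleeding is named once, for spontaneous bleeds of clinical significance. That item is one of several examples under a header covering adverse events that, in the investigator's judgement, prevent the participant from continuing. A separate item, without judgement wording, covers any situation in which continuing might put the participant at risk.

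**Section 6.6.** The first bullet reads "Management of bleeding events: in case of planned surgery with clinical significant bleeding risk" and goes on to require interruption before surgery and to permit restart after recovery. A general clause then permits interruption for other reasons if, in the investigator's opinion, "a participant is deemed to be at a significant safety risk unless administration of investigational treatment is temporarily interrupted". Restart is allowed at the next scheduled visit once the risk has resolved. Neither bullet nor clause mentions the rule in 4.5.

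**The concern.** Bleeding is a named potential risk of this drug, and 4.5 relies on stopping rules as part of its mitigation. Suppose a participant has a significant bleed after an injury or a procedure. Under 4.5 that participant stops drug for good. A site that turns instead to 9.1.1 and 6.6 finds an explicit bleeding item that does not describe this bleed, and a general permission to interrupt and then restart. Following 6.6 alone, the site could re-expose a participant whom 4.5 says must stop, and might not notice the deviation.

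What is at stake is the safety of the individual participant and consistent handling across sites. On the reporting side, four outputs could differ according to which section a site followed: the action taken for the event, adverse events leading to discontinuation, treatment disposition and duration of exposure.

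**Working it through.** The plan states no figure for this point, so the main check is a comparison of text.

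| Place | Which bleeds | Who decides | Action |
|---|---|---|---|
| Protocol 4.5 | Any significant bleed | No judgement wording | Immediate discontinuation |
| Table 6-2, anticoagulant and anti-platelet rows | Any significant bleed, in users of those drugs | No judgement wording | Immediate discontinuation |
| 9.1.1, bleeding item | Spontaneous and clinically significant | Investigator, through the header | Discontinuation |
| 9.1.1, safety-risk item | Bleeding not named | No judgement wording, but the risk has to be assessed | Discontinuation |
| 6.6, first bullet | Planned surgery with bleeding risk | Required | Interruption, then restart |
| 6.6, general clause | Any significant safety risk; bleeding not excepted | Investigator's opinion | Interruption, then restart |

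1. *Is the stop in 4.5 permanent?* The sentence does not contain that word. It follows from the definitions in the Glossary and 9.1.1, and from the separate use of interruption and discontinuation in Table 6-2.
2. *Does 4.5 bind sites?* Yes. Under Section 13.2 the investigator signs to follow all of the protocol's instructions.
3. *Which case is not aligned?* A significant bleed that is not spontaneous. It falls under 4.5 and outside the explicit bleeding item in 9.1.1, and the general clause in 6.6 does not exclude it.
4. *How common is it?* The documents give no rate. The exclusion criteria in Section 5.2 should make it rare. They include "Major surgery within 8 weeks prior to screening or planned surgery for the duration of the study" and "Significant bleeding risk or coagulation disorders", as well as a need for anticoagulants.
5. *Does it affect the primary endpoint?* Hardly. A bleed that starts on treatment and is recorded as an adverse event already counts that participant once in the overall proportion.

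**Cost of the fix in one-year exposures** (Protocol 12.8; SAP Section 3). The target is at least 100 Japanese patients treated for one year.

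- Expected completers here: 70 × (1 − 0.15) = 59.5, which the plan gives as approximately 60.
- Planned total: 33 + 15 + 60 = 108, so the margin is 108 − 100 = 8.
- With 59.5 in place of 60: 33 + 15 + 59.5 = 107.5, so the margin is 7.5, or 7 whole participants.

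This assumes that the other two studies deliver their planned 33 and 15.

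**The case against.** The strongest reply is that nothing truly conflicts. Section 4.5 is specific and mandatory, while 6.6 is a restrictive permission under which restart is optional, so 4.5 governs. Section 9.1.1 is also wider than its bleeding item. Its list of adverse events is introduced as examples, the safety-risk item carries no judgement wording, and the investigator must in any case stop drug when continuing would harm the participant's well-being. These arguments stand, and they rule out the stronger reading that a reader might infer, namely that the protocol has no stop rule for traumatic or procedural bleeds. It has one in 4.5, and 9.1.1 can reach such bleeds. The objection leaves one thing unanswered: a site using 9.1.1 and 6.6 is not told that the stop is mandatory, and 6.6 offers restart for a similar trigger.

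A second reply is that a significant bleed has no stated criteria in these sections, so 4.5 itself needs judgement. That is correct, and no wording will make the stop fully automatic. Section 4.5 refers to the Investigator's Brochure for further detail, so criteria may exist there. Still, judging whether a bleed is significant differs from judging whether a participant who has had one may continue, and 4.5 leaves only the first open.

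A reader might also cite the platelet threshold in 9.1.1 as proof that the list separates automatic stops from judgement calls. Appendix 1 does not support this: for the same value, once confirmed, it says only that discontinuation should be considered.

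Finally, the core Phase 2b study reported no serious or severe bleeding (Section 4.5). That supports rarity but does not settle which section a site should follow.

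**Conclusion.** The inconsistency is real and modest. The rule in 4.5 is not carried into the bleeding item of 9.1.1 or excepted from the restart clause of 6.6, so a site could restart drug after a significant non-spontaneous bleed in breach of 4.5. It should be corrected because the rule protects participants and alignment is cheap.

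No number of affected participants can be given, and none is claimed. The conclusion rests on reading discontinuation as the protocol defines it, and on the text of the protocol alone; criteria in the Investigator's Brochure could clarify what counts as significant. A reader might infer that the primary safety result is at risk. The documents do not support that, because the bleed itself already places the participant in the count. The effect is confined to the handling of individual cases and to the related summaries of action taken, discontinuation, disposition and exposure.

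**What to change.** - **Section 9.1.1:** add a stand-alone item outside the investigator-judgement header, for example *Significant bleeding event, spontaneous or not (see Section 4.5)*, with a pointer to any criteria for significance in the Investigator's Brochure.
- **Section 6.6:** state that the general interruption-and-restart clause does not apply to significant bleeding events. Leave the planned-surgery interruption as it is.

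The change needs protocol wording and a note to sites, and no new procedure. The downside is that a rare participant with a significant non-spontaneous bleed stops drug permanently instead of restarting, which loses a little one-year exposure against the planned margin of about 7 to 8.

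If the sponsor does intend restart after such bleeds, the alternative is to narrow 4.5 and Table 6-2. That would loosen a stated safety rule and should be a deliberate, justified decision.
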